7.7 The identification of any data to be recorded directly on the CRFs

Data that will be included directly on the electronic CRF will be:

- Randomisation code
- Dates tablets sent
- Dates study documents are sent and returned (consent forms, surveys)
- Adverse events
- Withdrawals (including date, reason for withdrawal)

8 Description of the population to be studied

Residents of Australia (with the exception of the Northern Territory) aged between 60 and 79 years will be selected at random from the Commonwealth Electoral Roll. Selection will be stratified by region, age (in 5-year age bands) and sex to ensure an approximately equal region, age- and sex-distribution. Volunteers will be able to participate in the trial and their region, age- and sex- distribution will be monitored to inform the selection from the electoral roll. We aim to recruit 25,000 participants.

8.1 Inclusion criteria

- Aged 60 to 79 years old (randomly selected electors). Aged 60 to 84 years old (volunteers)
- Enrolled to vote
- Do not have any of the health conditions listed below and are not cognitively impaired
- Are not taking vitamin D at doses >500 IU/day

8.2 Exclusion criteria

People will be excluded if they are unable to give consent or to communicate well enough in English to understand study materials or if they indicate in an initial screening form that they:

- Have any of the following medical conditions (which either preclude or require high dose vitamin D supplementation or which prevents informed consent: hyperparathyroidism, sarcoidosis, osteomalacia, a history of renal calculi, a history of high calcium.
- Are taking vitamin D at doses > 500 IU/day
- Cognitive impairment
- Do not have a telephone (landline or mobile)

8.3 Approach to potential participants/ obtaining consent

The initial approach to participants will be outsourced to Datatime Services Pty Ltd (Datatime). They will send an invitation to potential participants, enclosing an 'Expression of Interest' (EOI) form on which people who express an interest in taking part will be asked to answer several questions to determine eligibility and to provide full contact details. Those eligible will be posted a full information booklet, a trial consent form, a Medicare consent form, a baseline survey and a reply-paid envelope. Once the trial consent form and baseline survey are returned (either by mail or online – see below) participants will be formally entered into the trial and randomised. The Medicare consent form is optional.

If potential participants do not return their baseline survey and consent form within approximately two weeks of mailing, Datatime will send a reminder email (for those who provided an email address on the EOI) or

postcard (for those people with no email address). Those who do not contact the study team or return the forms within approximately two weeks of the reminder being sent will be followed up by telephone by members of the study team at QIMR Berghofer.

8.3.1 Volunteer recruitment

Volunteers will be able to participate in the D-Health Trial. If a volunteer contacts the study via telephone an EOI form will be completed over the telephone and subsequently entered in the database. If the participant is eligible they will be asked if they would prefer to do the consent and baseline survey online or via paper. If the former, the link to the website (with study ID and password) will be emailed to the participant. If they would prefer to complete the paper consent form/s and survey their details will be provided to Datatime who will manage their recruitment in the same way as those selected from the electoral roll. If a volunteer emails the study we will ask them to provide us with a telephone number so that we can contact them to undertake this process.

We will invite those participants who took part in the pilot trial, **and who said they would have been willing to continue** if the trial had continued.

8.3.2 Online consent protocol

- 1. DataTime will send a letter of invitation to selected potential participants (selected at random from the Australian Electoral Roll), enclosing an "Expression of Interest" (EOI) form. Participants can choose to complete this form online by entering their study ID into the online EOI.
- 2. Participants who meet the eligibility requirements will be directed to the online information booklet. They will be asked to confirm that they have read the information booklet, and will then be directed to the consent form.
- 3. The participant will be asked to fill in all the required details, type their name into the signature field and insert the date that the form was signed.
- 4. A second consent form will appear, asking for consent for release of Medicare data. The participant will be asked to complete necessary fields for Medicare, and to click a button confirming consent. The Medicare consent is not required for participation in the study.
- 5. An email will be generated automatically and sent to the participant ("Acknowledgment of Consent"); a pdf copy of the consent form/s will be attached. A copy of the form/s will also be sent to the D-Health email address.
- 6. After completing the consent forms, the participant will be taken straight to the survey page.
- 7. The "Acknowledgment of Consent" email will also contain a link to the survey page so that the participant can access this at a later time.
- 8. The participant will click on the link and complete the survey online.
- 9. Once completed another email will be generated and sent to the participant acknowledging completion.

The online database will meet stringent security standards (see appendix 1).

8.4 Participant withdrawal

Participants can withdraw from the study, defined as stopping the intervention, by informing us in writing or by telephone or email. Participants who cease taking tablets will be invited to continue completing surveys. Unless specifically requested in writing, we will link all participants to health registers during routine linkages. Participants do not have to give a reason for their withdrawal. Information already collected will be destroyed at their request.

Participants will be withdrawn at the time of notification if they are diagnosed with kidney stones or sarcoidosis or experience a suspected unexpected serious adverse reaction (SUSAR). Patients diagnosed with hypercalcaemia or hyperparathyroidism will also be withdrawn unless a cause has been identified and treated

and the serum levels of calcium and PTH have returned to normal. A decision about whether to withdraw the participant will be made in consultation with the study physician. While we would prefer that participants not take more than 500 IU of off trial vitamin D per day, once enrolled they will only be withdrawn if they take vitamin D supplements at greater than 2000 IU/day as (if they are in the intervention arm) this will cause them to exceed the safe upper intake level of 4000 IU/day.

The following information will be captured in the D-Health Trial database for all participants who withdraw/ are withdrawn from the study:

- Date of withdrawal
- Reason for withdrawal: (including an option for no reason given)
- Willing to keep completing surveys: yes / no
- Willing for us to keep information already collected: yes / no (details if any caveats)
- Willing for us to obtain information in the future: yes / no (details if any caveats)

No withdrawn participants will be replaced.

9 Trial Treatment and Processes

9.1 Dose and dosage regimen

Participants will randomised to take either 60,000 IU of cholecalciferol or placebo orally each month for 5 years.

9.2 Formulation

Gelcaps packed in blister packs of 12

1. Active tablet: The vitamin D used in the D-Health Trial will be cholecalciferol, 60,000 IU taken as a single tablet once per month. It will be supplied in blister packs. It is stable at room temperature. Formulation is as follows:

Cholecalciferol: From Vitamin D3 1.0 m IU/g (ARTG No 1335) 60mg (equivalent to vitamin D3, 60,000 IU). 20% overage.

Other ingredients: soya oil (181.6mg), DL-alpha tocopheryl acetate (16.4mg), softgel capsule (glycerol, gelatin, titanium dioxide, purified water)

2. Placebo: soya oil (253.6mg), DL-alpha tocopheryl acetate (16.4mg), softgel capsule (glycerol, gelatin, titanium dioxide, purified water)

Note: The addition of alpha tocopheryl acetate is to increase the stability. Lipa pharmaceuticals manufactured the placebo and vitamin D3 (cholecalciferol) gel capsules for the D-Health Trial. The starting content of the vitamin D tablets was ~72,000 IU cholecalciferol. There has been a decreasing trend and by 12 months the content was ~47,000 IU cholecalciferol. Lipa investigated the content of the tablets using HPLC methods and concluded that the vitamin D3 has isomerised to pre-vitamin D3. They used a formula from the British Pharmacopoeia to determine that the pre-vitamin D3 equivalent quantity is 23,677 IU and that the total vitamin D per capsule is 70,467 IU. Nevertheless the product is being remanufactured using a formula previously shown to be stable in the D-Health Pilot Trial (P1294) and will be dispensed from June, 2015.

The dispense module of the D-Health database is designed such that the batch of tablets being dispensed is recorded in the participant record.

9.3 Packaging and labelling

One blister pack containing 12 gelcaps will be supplied at the beginning of the trial and every 12 months thereafter for the duration of the trial. Participants will be asked to take one gelcap each month, and will be sent automated reminders (telephone, text or email). All product will be labelled:

D-Health Study Capsules For Clinical Trial Use Only		
ID Number		
Name		
Dose: Swallow one tablet each month		
These capsules contain placebo or cholecalciferol (vitamin D3) (60,000 IU). Store at room temperature QIMR Berghofer Medical Research Institute P1519, [name] In emergency contact [name]		
Use By: / /		
Keep out of reach of childrenBatch #No of tablets: 12Date		

9.4 Description of and Justification for the route of administration, dosage, dosage regimen and treatment periods

The D-Health pilot trial showed that 60,000 IU / month was needed to shift the population distribution to a mean of 75 nmol/L. This equates to an intake of 2000 IU/day which is well within the tolerable upper intake level of 4000 IU / day set by the IOM.

Evidence suggests that patients prefer intermittent rather than daily dosing, and that this may lead to higher compliance ⁴⁷. A pharmacokinetic study of a single dose of 100,000 IU in people with mean baseline 25D of 67 nmol/L found that serum levels remained above 80 nmol/L for more than 2 months ¹⁵. A comparison of the same average daily dose (1,500 IU) given daily, weekly or monthly found that dosing monthly was as effective as daily dosing in maintaining serum levels ⁴⁸. We have therefore selected oral monthly dosing as the most cost-effective way of maximising compliance.

We have chosen an intervention period of 5-years. While there is no concrete data on which to base a decision about the length of the intervention, it appears likely that vitamin D contributes to disease processes later in life. The mean trial size-adjusted intervention period in the meta-analysis of trials with mortality as an outcome was 5.7 years.

9.5 Monitoring participant compliance

Participants will be sent surveys annually. In the surveys participants will be asked to report the number of tablets taken, and whether they have started taking off-label vitamin D supplements. If participants do not return the survey we will follow-up by telephone. If the participant indicates that they do not plan to complete the survey, we will attempt to obtain information about compliance over the telephone and enter this directly into the D-Health Trial database.

9.6 Blood collection

We will obtain blood samples (8ml tube) from approximately 600 participants (300 from each of the study arms), selected at random each year. Each month approximately 3% of participants (to allow for non-

participation) will be selected (by computer-generated random number). With their annual survey they will be sent an invitation to donate blood, a blood PICF, a short one-page survey (D-Health Blood Collection Participants' Survey), and a request form to take to a participating pathology laboratory to have blood drawn. Participants will be provided with a copy of the consent form to keep. The blood will be returned to QIMR Berghofer for processing. If the consent form does not arrive, we will telephone the participant and ask for it to be returned. If the participant is not able to return the form for some reason we will obtain verbal consent over the telephone. This will be witnessed by another QIMR Berghofer staff member.

Blood will be processed and stored in a -80°C freezer..

9.6.1 Serum vitamin D measurement

One serum aliquot will be used for estimation of serum 25D – testing will be performed by a laboratory that is taking part in international standardisation program or by a commercial clinical pathology laboratory.

The laboratory will provide results to an independent statistician who will provide a summary report (mean, median, range, interquartile range) for each group, without group labels attached. To ensure the laboratory remains blinded, the study group label provided to the laboratory will differ each year (eg year 1 will be A and B; year 2 will be P and Q). The statistician will provide the DSMB secretary with a list of ID numbers for participants with a serum 25D of less than 25 nmol/L (frank deficiency). S/he will access the database and send out a standard letter to these participants advising them of their low vitamin D level and recommending that they seek medical advice.

9.6.2 Studies of vitamin D and health

Samples collected, processed and stored according to the above procedures may also be used to investigate the effects of vitamin D on health factors such as cholesterol and blood sugar. If studies are conducted of factors that may have clinical significance we will ask participants if they would like to receive their results – if so, these will be communicated to their nominated general practitioner.

Samples will be stored to enable extraction of DNA that will be used to investigate the effects of vitamin D on health. For example, we may investigate the effect of vitamin D supplementation on epigenetic factors or telomere length. We may also contribute to pooled analyses investigating the effect of common polymorphisms on response to vitamin D supplementation.

The genetic research conducted will almost certainly not have any clinical relevance – results will therefore not be communicated to participants. If studies of genetic factors known to important to health are proposed consent will be sought.

Samples (with or without data) may be provided to external researchers for studies of vitamin D and health. These studies will have to be approved by the scientific advisory board, the QIMR Berghofer HREC and the institutional review board or the HREC of the institution requesting the samples. The D-Health Trial data manager will provide a dataset containing approved data items to the requesting scientist, along with approved blood samples.

9.6.3 Risks of blood collection

The risks associated with having blood collected are low but include:

- Excessive bleeding
- Fainting or feeling light-headed
- Haematoma
- Infection

We will minimise these risks by asking participants to have blood drawn at pathology collection centres who employ qualified phlebotomists.

9.7 Drug supply and distribution / accountability

The tablet manufacturing company will supply gelcaps to QIMR Berghofer in boxes labelled A or B. Blister packs will be identified with an A or B.

When a participant is randomised a letter will be generated which will be inserted into a window-faced envelope with the participant name and address displayed. A label will be generated for the blister packaging (as above). One research assistant will label the product and insert it into the envelope. A second research assistant will check that the correct product has been dispensed and appropriately labelled, and will confirm that they have checked by recording a digital signature in the database.

The D-Health Trial database will contain an up-to-date log of dispensed materials.

The IP will be held at room temperature in a secure QIMR Berghofer facility that has temperature logging enabled.

10 Measurement of outcomes

Information will be collected by surveys and data linkage with state and national health registers for up to 10 years after the intervention phase of the trial ends.

10.1 Surveys

At baseline participants will be asked about their past medical history, recent sun exposure, sensitivity of skin to the sun, intake of foods rich in or usually fortified with vitamin D, and use of nutritional supplements (with specific nomination of vitamin D). At 12 months after enrolment, each participant will be sent a survey that focuses on health events during the previous 12 months (for example but not necessarily exclusively, osteoporosis, cardiovascular disease, cardiovascular events, fracture, diabetes).

Measurement of cognition; Cognition cannot be measured using self-administered surveys. We will therefore assess this outcome as part of our annual surveys using the Telephone Interview for Cognitive Status (TICS) which is licensed by Psychological Assessment Resources Inc.

Participants will be sent a letter with their survey letting them know that we are doing an assessment of memory and thinking as part of the survey and that this will be done using a telephone interview. They will be able to opt out of this component and still participate in the trial. Unless the participant has opted out by phone, email or letter, a member of staff will telephone in the 4-6 weeks after the survey has been mailed to administer the TICS.

Measurement of cognition will be restricted to people aged over 70 years at the time of the first assessment (planned to be administered as part of the second annual survey). People who participate in the first TICS interview will be invited to take part a second time as part of their fourth or fifth annual survey.

The TICS was designed for use in epidemiological surveys and is not routinely used as a diagnostic tool. We will therefore not provide participants with their TICS score, but will advise them to seek advice from their general practitioner if they feel that they are experiencing cognitive problems. Similarly, if participants become distressed during the interview they will be reminded that the TICS is not a diagnostic tool and advised to discuss their concerns with their general practitioner.

Sample size for cognition outcome: A previous study has analysed temporal changes in TICS score. In that study, people aged 65 years and over with two long-lived parents had a decline in the TICS score of 0.14 per year; those with no long-lived parents had a decline of 0.24 - a difference of 0.1 per year. Since the prevalence of dementia doubles every five years after age 65 and we are restricting our interview to participants aged

over 70 years or older, a faster rate of decline is likely. We therefore hypothesise that a decrease of 0.3 in the TICS score per year will occur in the placebo group and that a difference of 0.2 per year in the rate of decline in the TICS score in the treatment group (i.e. a difference of 0.4 after the first two years of supplementation) would constitute a relevant difference in cognition.

Previous studies have shown that the standard deviation of the TICSm score ranges from 3.8 to 4.7.⁴⁹⁻⁵¹ Assuming the standard deviation will be approximately 4.5, a sample of 3976 (n=1988 per group) will result in 80% power to detect a difference of 0.4 in the TICS after two years.

Measurement of falls: The gold standard approach to measurement of falls is to ask participants to complete a falls diary. We will ask a subgroup of participants to complete falls diaries to supplement the questions we ask in our annual surveys.

Eligibility: Participants who are in the trial and are aged over 70 on the date of the selection will be eligible to participate in the falls component of the trial.

Process: We will mail an invitation to complete a falls diary, along with a falls diary, a magnet to affix the diary to a magnetic surface such as the fridge, and a reply-paid envelope. We will ask participants to contact us if they would prefer not to participate.

Participants will be asked to begin the diary on the first day of the following month and to complete the diary each day for 3 months. We will send reminders to complete the diary every 2-4 weeks using the mode/s (text, landline, email) that we currently use to send tablet reminders. At the end of the 3-month period we will remind participants to return the diary in the reply-paid envelope.

Recruitment will occur over several months to ensure capacity to manage this component of the trial.

Sample size: The sample size has been decided in consultation with the data safety monitoring board and they have approved this strategy. A sample size of 400 in each group will provide 80% power to detect a risk ratio of 1.8. We will recruit 500 people in each group to allow for loss to follow-up. If a participant declines to participate they will be replaced with another randomly selected participant of the same age group (5 year age category) and sex.

Data analysis: We will use an intention-to-treat analysis to compare: (1) the proportion of people who fall in each group; (2) the total number of falls in each group. We will use multivariate regression models (logistic and poisson), adjusted for age and sex to improve the precision of the estimates. We will categorise falls according to their severity. Due to lack of power, analyses of severity will be descriptive.

Measurement of acute respiratory infections (ARI): The gold standard approach to measurement of ARI is to ask participants to complete an ARI symptom diary. We will ask a subgroup of participants to complete symptom diaries for 8 weeks in winter/early spring to supplement the questions we ask in our annual surveys.

Eligibility: Participants who are in the trial on the date of the selection will be eligible to participate in the ARI component of the trial.

Process: We will mail an invitation to complete an ARI symptom diary, along with the diary, and a reply-paid envelope. We will ask participants to contact us if they would prefer not to participate.

Participants will be asked to begin the diary on the first day of the following month and to complete the diary each week for 8 weeks during winter. We will send reminders to complete the diary every 2-4 weeks using the mode/s (text, landline, email) that we currently use to send tablet reminders. At the end of the 8-week period we will remind participants to return the diary in the reply-paid envelope.

Sample size: A sample size of 1430 in each group will provide 80% power to detect a rate ratio of 1.8. We will recruit 1600 people in each group to allow for loss to follow-up. If a participant declines to participate

they will be replaced with another randomly selected participant of the same age group (5 year age category) and sex.

Data analysis: We will define ARI using the Jackson cold scale which takes account of both the number and severity of symptoms. We will use multivariate poisson regression models to compare the incidence of colds between the two study arms.

Blood Collection Participants' survey: 25(OH)D concentration is influenced by sun exposure, physical activity and supplementation. To enable validation of a model to predict vitamin D status (based on 25(OH)D concentration) we will ask participants providing a blood sample to complete a short one-page survey (Blood Collection Participants' survey).

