14.2 Statistical analysis

We will use intention-to-treat analyses to assess the effect of vitamin D supplementation on all endpoints. Use of the Cox proportional hazards model will allow for variable follow-up lengths and estimation of hazard ratios for mortality and other events obtained from linkage. For outcomes such as falls, fractures and nonmelanoma skin cancer where events can occur more than once, we will use Poisson or negative binomial models (depending on the distribution) to model the number of events. Endpoints that are measured on a continuous scale and that cannot be captured through passive monitoring will be assessed using linear regression models, with analyses to estimate the effects of differential loss-to-follow-up and therefore differences in patient-reported outcomes.

In exploratory analyses we will evaluate effect modification by age, sex, baseline risk factors, dietary calcium intake and predicted baseline vitamin D level (in our pilot data we were able to predict a baseline vitamin D level of less than 50 nmol/L with a C statistic of 0.7). The study has insufficient power for these stratified analyses, but we plan to pool our data with the Vital Study data (and possibly with the FIND data despite its different dose) to substantially increase the available sample size.

Interim analyses will occur after the first linkage (planned for 2017) and after subsequent linkages. Final analysis will be at approximately 5 years after the final participant has completed the intervention phase.

An analysis using Cox Proportional Hazards analysis will be conducted up to the time of change in the formulation of the tablets. This will supplement the final analysis across all time points as presently proposed. In addition, we will carry out some supplementary analyses that are not based on intention-to-treat principles. These will account for compliance and off-trial use of vitamin D (contamination), and we will incorporate time on the old versus the new formulation into these analyses.

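### Section 10.1 names only Poisson regression for the falls-diary and ARI-diary counts, which is narrower than section 14.2 and would understate standard errors if repeat events cluster within people

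*Protocol*

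**What the plan says.** Protocol section 10.1 sets up two diary components.

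- **Falls diary** (three months, participants over 70). Two comparisons are planned: "1) the proportion of people who fall in each group; (2) the total number of falls in each group". The models are "multivariate regression models (logistic and poisson), adjusted for age and sex to improve the precision of the estimates". Logistic regression serves the first comparison, so Poisson is the only model named for the count.
- **ARI diary** (eight weeks). One model is named: "We will use multivariate poisson regression models to compare the incidence of colds between the two study arms".

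Neither paragraph mentions dispersion, the variance estimator or an alternative count model.

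Section 14.2 gives a general rule. "For outcomes such as falls, fractures and nonmelanoma skin cancer where events can occur more than once", it says, "we will use Poisson or negative binomial models (depending on the distribution) to model the number of events". Falls are listed there. ARI is not, although the list is open-ended.

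On size, section 10.1 states for falls: "A sample size of 400 in each group will provide 80% power to detect a risk ratio of 1.8", and for ARI: "A sample size of 1430 in each group will provide 80% power to detect a rate ratio of 1.8". It gives no baseline risk, baseline rate or dispersion for either.

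**The concern.** Poisson regression sets the variance of a count equal to its mean. If people differ in their risk of falling or of catching colds beyond what age and sex explain, the variance exceeds the mean. Model-based Poisson standard errors are then too small, intervals too narrow and p-values too low. Section 14.2 anticipates this for falls, but the diary paragraphs do not carry the provision over.

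Two features give the point some weight. Section 4 motivates the falls work by possible harm at high intermittent doses. Section 13.4 routes diary-captured falls into biannual safety reports that include significance assessments between arms, though it does not say which test is used. In addition, section 14.4 requires departures from the original statistical plan to be justified. Having named Poisson, the team might have to defend a change of model after seeing the counts.

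**Working it through.** **Inputs from the protocol (section 10.1).** Falls: 400 per group, ratio 1.8, power 80%, 500 recruited. ARI: 1430 per group, ratio 1.8, power 80%, 1600 recruited. Section 14.1 uses a significance level of 0.05 for the main trial; I assume it carries over, two-sided.

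**Step 1. The plan's own sample sizes.** With no baseline given they cannot be reproduced forwards, so I solved for the baseline they imply.

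- Falls as two proportions: 400 per group at a risk ratio of 1.8 corresponds to a control risk of about 7.6% (8.2% with continuity correction). The recruitment target fits 20% loss: 400/(1 − 0.20) = 500.
- Both as Poisson counts: n = (1.960 + 0.842)² × (1/m + 1/(1.8m)) / (ln 1.8)², so m = 7.849 × 1.5556 / (0.3455 × n). For n = 400, m = 0.088 falls per three months. For n = 1430, m = 0.025 colds per eight weeks. The ARI recruitment target allows 1 − 1430/1600 = 10.6% loss.

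**Step 2. Effect of dispersion.** For negative binomial counts with parameter k, variance/mean is φ = 1 + k × m. Poisson standard errors are too small by √φ, and the true type I error is 2(1 − Φ(1.96/√φ)). All values of k are assumptions.

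| Diary | Mean | k | φ | True type I error |
|---|---|---|---|---|
| Falls | 0.088 (implied) | 0.5 | 1.04 | 0.055 |
| Falls | 0.088 | 1 | 1.09 | 0.060 |
| Falls | 0.088 | 2 | 1.18 | 0.071 |
| Falls | 0.088 | 4 | 1.35 | 0.092 |
| Falls | 0.2 (assumed) | 2 | 1.4 | 0.098 |
| Falls | 0.3 (assumed) | 2 | 1.6 | 0.121 |
| ARI | 0.025 (implied) | 0.5 | 1.01 | 0.051 |
| ARI | 0.025 | 4 | 1.10 | 0.062 |
| ARI | 0.2 (assumed) | 1 | 1.2 | 0.074 |
| ARI | 0.5 (assumed) | 1 | 1.5 | 0.110 |

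**Step 3. Simulation check.** Negative binomial counts at 400 per group, tested with the Poisson standard error, rejected a true null in 0.056 of runs (mean 0.09, k = 1), 0.066 (0.09, k = 2), 0.080 (0.15, k = 2), 0.096 (0.2, k = 2) and 0.120 (0.3, k = 2). This agrees with the formula.

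**Step 4. Could rates exceed the implied means?** Section 4 cites a trial in people at high risk of falling in which 48% to 67% fell over 12 months. At a constant rate that is −ln(0.52)/4 = 0.16 to −ln(0.33)/4 = 0.28 falls per three months. This is a rough guide only. D-Health participants were not selected for fall risk, which would make their rate lower. The conversion also ignores differences between people, which makes it too low for the trial cited.

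**Step 5. Power for falls.** Adding 2k to the bracket in the step 1 formula gives the negative binomial sample size. At mean 0.088 and k = 0.5, 1, 2 and 4, power at 400 per group is 0.78, 0.76, 0.72 and 0.64, and 80% power needs 423, 446, 491 and 582 per group.

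**The case against.** The strongest reply is that the protocol already covers this. Section 14.2 names falls and keeps negative binomial open. Poisson is one of the two models it permits, so section 10.1 can be read as shorthand. A reader might infer that the two sections contradict each other; they do not, since 10.1 is only narrower. The open wording of 14.2 can also be read to include repeat colds.

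A reader might also infer that section 10.1 commits to Poisson with uncorrected standard errors. The text is silent on the variance estimator, and a statistical analysis plan could specify a robust one without departing from 10.1.

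A third tempting reading is a much larger error: variance/mean of 1.5, 2 or 3 gives a type I error of 11%, 17% or 26%. The arithmetic is right, but at the implied falls mean those ratios need k of about 5.7, 11 and 23 (0.5, 1 and 2 divided by 0.088). At the implied ARI mean they need about 20, 40 and 80. The documents offer no support for such values.

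Finally, it might be supposed that the safety board asked for the falls work. Section 10.1 says only that the board was consulted on the sample size and approved the strategy.

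These replies limit the point without removing it. Section 10.1 does name a model, it is the one that fails under clustering, and ARI is not listed in section 14.2.

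**Conclusion.** The point holds as a mismatch to harmonise. For both diary counts section 10.1 names only Poisson, without the alternative that section 14.2 keeps for recurrent events. If counts are overdispersed and model-based errors are used, the true type I error at the implied means is about 5.5–9% for falls and 5–6% for ARI (k = 0.5–4). It is about 10–12% for falls at means of 0.2–0.3 with k = 2, and 7–11% for ARI at means of 0.2–0.5 with k = 1. Dispersion and the higher means are assumptions; the implied means depend on the 0.05 two-sided level.

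ARI is the weaker part at its implied mean. The comparison of the proportion who fall is untouched, and the falls sample size, stated as a risk ratio, fits that comparison. Priority is minor: section 6 lists falls and upper respiratory illnesses as tertiary outcomes, and the diaries are completed by subgroups to supplement the annual surveys.

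**What to change.** In section 10.1, replace the Poisson wording for both diary counts with one pre-specified analysis: negative binomial regression, or Poisson regression with robust variance, with log diary time as offset and adjustment for age and sex. Cross-refer to section 14.2 and add ARI to its list of recurrent outcomes. Leave the logistic comparison of fallers as it is.

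The cost is a line or two of text and no new data. Intervals widen on the log scale by √φ. That is about 2–16% for falls and 1–5% for ARI at the implied means with k = 0.5–4, and up to about 26% (falls, φ = 1.6) or 22% (ARI, φ = 1.5) in the higher-rate cases. If the counts are not overdispersed, they are almost unchanged.
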